1. Participant child is experiencing severe self-injurious behavior or severe aggressive behavior to self or others (within past 7 days).
2. Participant has been diagnosed with another psychiatric or neurological disorder (e.g. epilepsy) or have exhibited symptoms of major psychiatric disorders within the last 30 days.
3. Participant has an unstable medical condition (that requires clinical attention).
4. Participant has a significant skin condition at the procedure sites (i.e., hemangioma, scleroderma, psoriasis, rash, open wound or tattoo).
5. Participant has an implant of any kind in the head (e.g. stent, clipped aneurysm, embolised AVM, implantable shunt - Hakim valve).
- 6. Participant has receiving medication on a regular basis for Autism or any other medical condition.**
7. Any use of light-activated drugs (photodynamic therapy) within 14 days prior to study enrollment (in US: Visudine (verteporfin) - for age related macular degeneration; Aminolevulinic Acid- for actinic keratoses; Photofrin (porfimer sodium) - for esophageal cancer, non-small cell lung cancer; Levulan Kerastick (aminolevulinic acid HCl) - for actinic keratosis; 5-aminolevulinic acid (ALA)- for non-melanoma skin cancer).
8. Current treatment with a psychotropic medication.
9. Investigator and his/her immediate family, defined as the investigator's child or grandchild.

5.0 Sample Size:

30 children will be included in the study. We need at least 15 participants in the control condition, and 15 participants will receive a combined light and audio treatment therapy. These numbers will allow us to gain sufficient statistical power to detect small size systematic effect. **We anticipate to screen about 40 participants to recruit 30 participants for the study.**

We plan to screen more than 30 prospective children, because we expect some of them to be ineligible for the study, due to the above listed Exclusion Criteria. We plan to enroll 30 children, so that each group will have at least 15 participants. We do anticipate that some of the participants will withdraw, for various reasons. participant We will continue screening until we have 30 enrolled participants.

If a participant drops out of the Study we will attempt to replace that participant, using the same Eligibility Screening Criteria.

6.0 Research Locations:

[name]

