This is a private professional office, with a waiting room and a receptionist. There are several private rooms within the office.

The child will be led to a private room, which will have toys and books inside it. The caregiver and one of the researchers will be present in the room at all times.

[name]

This is a private professional office, with a waiting room and a receptionist. There are several private rooms within the office.

The child will be led to a private room, which will have toys and books inside it. The caregiver and one of the researchers will be present in the room at all times.

7.0 Procedures Involved:

7.1 Location: The study will use pre-test and post-test design. The entire study on the children will be done in the office. The weekly interview with the parent may be done either in office or by phone, as preferred by the parent.

7.2 Conditions: There are two conditions: placebo condition, and combined light and audio therapy treatment condition. The placebo control condition will listen to nursery rhymes. **The placebo control condition will wear the same device, however the lights are not going to be turned on. Otherwise, all experience for participants in control and experimental conditions will be identical.**

This study replicates and extends previous studies of photobiomodulation in children older than 5 years of age (Leisman et al, 2018).

7.3 Participants: The participants will be matched on age, gender and number of hours of therapy they receive independent from the study. The participants will be 24-71 month old children previously diagnosed with moderate or severe ASD. The experiment will use random assignment. We plan to use 30 participants (15 in each group). **We plan to screen about 40 participants (or fewer) to recruit the 30 participants for this study.**

7.4 Random Assignment: Random assignment will be achieved by using random number generator programs frequently used in research (such as random.org). Each participant is assigned a number. The list of 30 numbers is entered into the program, which creates a random sequence of 30 participants. Here is an example of the beginning of such list generated for 30 participants

1 – 23

2 – 25

1 – 12

2 – 15

1 – 21

2 – 5

1 – 19

2 - 9

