Once the program generates the random sequence of 30 participants (in the example above, the sequence goes 23, 25, 12, 15, etc), we will simply alternate the assignment to treatment and control conditions. For example, in the example above, participant number 23 is assigned to the treatment condition (1), and participant number 25 is assigned to the control condition (2). Because the sequence of the participants is randomized, the assignment to conditions is random.

7.5 Treatment: The treatment will take place twice a week for up to 30 minutes at a time.

During the study, while participants will be wearing the photobiomodulation device, they will be listening to the audio program, and they may be playing with their parent or the experimenter, using the toys of their choice (out of the many available in the experimenter’s office). The caregivers will be present during the experiment at all times. When the child and the parent arrive, they will be welcomed to the office, and introduced to the toys.

The child will be encouraged to play with toys and interact with the parent (or the experimenter). The children in the experimental condition will be asked to wear the device for no longer than 15 minutes. The children in the controlled condition will play for 30 minutes and wear the same device, without turning it on (the device won’t be turned on at that time). The total time in the office will be about 30 minutes (including playing).

If the child becomes uncomfortable, the parents will be able to leave the experiment without any punishment. No coercion or deception is involved in this study.

7.6 Pre and Post-Testing: CARS2 will be used for pretest and post-test. Please see attached a sample CARS 2 test. CARS 2 scores will be compared for analyses. **In addition, EEG will be collected from the participants in both Control and Experimental conditions pre and post -treatment (before Starting treatment in session 1 and in the end of treatment of Session 8). Mobile FDA approved EEG device Brain Scientific will be used to collect children's pre and post test EEG. There is no known danger of EEG collecting. In this study it will be using for measuring the efficacy treatment only.**

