7.7 On-going Data Collection: Parents will be asked to keep a daily diary of the child's behavior, specifically – words spoken, comprehension of instructions, eye contact, his sleep pattern, number of tantrums, anxiety, social interaction and eating. Qualitative data will be collected through short weekly interviews with the parents. These interviews can take place either in [name] office during the child's treatment or by phone. During those weekly interviews, the parents will be asked questions about their children's responsiveness to language, number of words they can produce, eye-contact, anxiety, frequency of tantrums, eating, and difficulties falling asleep and sleeping through the night. Please see attached proposed script for the weekly call. The qualitative data will be used to further inform and supplement quantitative data (total CARS 2 scores).

The study will collect qualitative and quantitative data. The quantitative data will be the total CARS2 scores of the participants of both Control and Treatment groups, obtained before and after the study is done. Mixed Design Analysis of Variance will be used to analyze quantitative data. **In addition, we will collect Before and After Prefrontal cortex EEG from the control and experimental treatment groups to measure electrophysiological changes in Prefrontal cortex. after treatment. EEG data will be analyzed (using Time-Frequency analysis), and after baseline normalization, the data will be used in aggregate to compare conditions numerically. The between group comparison before the treatment will be conducted using between subject T-test for each brainwave . The between group comparison will be conducted after treatment for each brain wave using between subject t-test. In addition, for the treatment condition only Before and After comparison will be conducted, using within subject t-test.** In addition, we will obtain qualitative data from weekly parental interviews, during which we will ask participants' parents about their children's behavior (see attached protocol). Qualitative data will be used for information purposes and will supplement quantitative data.

7.8 Blinding of the Researcher: [name] (the PI) will not be present in the room when the child is receiving the treatment. She will not be aware what group each particular participant has been placed in. [name] will be conducting the pre and post-testing interviews, as well as the on-going weekly interviews with the parents.

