Each participant (and their parents) has a right to withdraw from the study at any time. If a participant decides to withdraw from all components of a research study, we will discontinue interacting or intervening with the participant in order to obtain data about his or her participation in the study, we will not obtain additional identifiable private information about the participant for the research study from any source, and we will not obtain identifiable private information about the participant for the research study by observing or recording private behavior without interacting with the participant.

When a participant will inform us that he / she decides to withdraw, we will ask the participant to clarify whether the participant wishes to withdraw from all components of the trial or only from the primary interventional component of the trial. If the participant wishes to withdraw only from the primary interventional component, we may ask for permission to contact the participant to collect follow-up data about the child's behavior.

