	
interaction is extremely unlikely. The positive interaction (e.g., children becoming more responsive to ABA therapy) will also be monitored and recorded in parental diaries. The children should be able to receive their regular behavioral therapies while being enrolled in this study.

There may be risks that we do not know about yet. Exposure to LED lights is not known to have any negative side effects.
	
 • When the child will wear the headband, the child will be exposed to LED lights. The lights will be both red and near infra red. The lights will range in frequency

	
from 660 MHz to 850 MHz.
 
 • After years of study, there are no known negative side effects of photobiomodulation. • Throughout the study, we'll tell parents if we learn anything that might affect their decision to let their child participate.

Some participants may have to be withdrawn from the study
	
 • If the child is not able to attend all the required sessions and the caregiver is not able to reschedule a cancelled session within a 3 day window, then the child will have to be withdrawn from the study. • If the child becomes aggressive or self-injurious

	
during the session, then the child will have to be withdrawn from the study.
 
 • In that event, only the data that has been collected up to the date of withdrawal will be kept. • All identifying information will not be shared and all reports will be aggregated. • We will ask the child's parents for permission to contact them in the future with follow up questions regarding the child's behavior.

Furthermore, the study will be under oversight of [name], who is a board-certified pediatric psychiatrist with more than 10 years of experience working with children with ASD
	

14.0 Provisions to Protect the Privacy and Confidentiality of Participants and the Research Data:

Participants will be only interacting with [name] or [name], Esq. Participants and their parents will be tested individually, in a quiet room, and their confidentiality will be protected, as they won't be interacting with each other or with anybody else outside of the researchers.

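### The protocol plans no end-of-study CARS for a child who stops and no allocation rule for a replacement, so its written rules can bias the CARS difference if leaving relates to arm and outcome; for the data already reported this is a query

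*Protocol*

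**What the plan says.** - **Withdrawals are expected.** Protocol 5.0: "We do anticipate that some of the participants will withdraw, for various reasons".
- **What is kept.** Protocol 13.0 requires withdrawal when a missed session is not made up within 3 days, or when the child is aggressive or self-injurious in a session. It then adds: "In that event, only the data that has been collected up to the date of withdrawal will be kept".
- **Follow-up after stopping.** Protocol 8.0 (Withdrawal from the Study): "If a participant decides to withdraw from all components of a research study, we will discontinue interacting or intervening with the participant". A family leaving only the intervention may be asked to allow later contact about behaviour. Section 13.0 has a similar request. Neither names CARS.
- **When CARS is taken.** Protocol 7.7 has total CARS2 scores "obtained before and after the study is done". The SAP (Primary Analyses) places the final rating straight after the last treatment session.
- **Replacement.** Protocol 5.0: "If a participant drops out of the Study we will attempt to replace that participant, using the same Eligibility Screening Criteria".
- **Allocation.** Protocol 7.4: "The list of 30 numbers is entered into the program, which creates a random sequence of 30 participants", and then "we will simply alternate the assignment to treatment and control conditions". Sections 7.3 and 14.0 also mention matching on age, gender and therapy hours.
- **Reported result.** SAP (Primary Outcome): 16 Active and 14 Sham children, a difference in change of 7.23 (95% CI 2.357 to 12.107), and no missing post-treatment CARS among those who completed.

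**The concern.** A before/after comparison needs both scores. A child who stops has a baseline score and no planned endpoint, and a newly recruited child fills the gap. The visible text defines neither an analysis set nor a method for missing data. The inference is that, with the rules followed as written, completers and replacements are compared, not the children randomised.

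That is harmless if leaving is unrelated to arm and outcome. It matters if it relates to both, and some routes out overlap with what CARS measures. In-session aggression or self-injury is one. Sudden regress (Section 15.0) and a parent-reported change in how the child relates to or benefits from ABA (Section 13.0) are others, although the data-retention sentence does not extend to these two. Losing poor Active outcomes would enlarge the difference; losing poor Sham outcomes would shrink it. With no later CARS, nobody could check which had happened.

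**Working it through.** **1. Reported result.** Inputs are from SAP, Primary Outcome.
- Difference from the means: (43.5 − 33.7) − (40.6 − 38.0) = 9.8 − 2.6 = 7.2, against 7.23 stated.
- SE = [(12.107 − 2.357)/2] / t(0.975, 28 df) = 4.875/2.0484 = 2.380.
- t = 7.23/2.380 = 3.04, p = 0.005 (stated as 0.01).
- SD of change = 2.380/√(1/16 + 1/14) = 2.380/0.3660 = 6.50, assumed equal in both arms.

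The figure reproduces as an analysis of the 30 children with a final CARS.

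**2. What the rule itself can do.** The documents give no withdrawal rate, so every loss fraction q is an assumption. Setting: no true effect, 15 per arm, normally distributed changes with SD 6.50, pooled t-test, leavers from one arm only and replaced by children who stay.
- *Graded selection:* only children with below-average change leave, at random among themselves. Shift = SD × 0.798 × q/(1 − q).
- *Ceiling:* exactly the worst fraction q leave. Shift = SD × φ(z_q)/(1 − q). No stronger selection is possible at that loss rate.

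| Loss in one arm | Graded shift | Type I error | Ceiling shift | Type I error |
|---|---|---|---|---|
| 10% | 6.50 × 0.798 × 0.1/0.9 = 0.6 | about 6% | 6.50 × 0.1755/0.9 = 1.3 | about 8% |
| 20% | 6.50 × 0.798 × 0.2/0.8 = 1.3 | 8-9% | 6.50 × 0.2800/0.8 = 2.3 | about 17% |

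Type I errors are simulated. The sign follows the arm that loses the children. Leaving unrelated to outcome, or the same selection in both arms, gives a shift of 0 and a type I error of about 5%.

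**3. What a few unseen leavers would do to the reported result.** Add k hypothetical children with change c to one arm. For Active, the new mean is (16 × 9.8 + k × c)/(16 + k). The pooled sum of squares, 28 × 6.503² = 1184.1, grows by [16k/(16 + k)] × (9.8 − c)². Sham is treated in the same way, with 14 and 2.6.
- Two Active at zero change: 156.8/18 − 2.6 = 6.11. Sum of squares 1184.1 + 1.778 × 9.8² = 1354.9, SD 6.72, SE 2.395. Result 6.1 (95% CI 1.2 to 11.0, p = 0.016).
- Two Active worsening by 5: (156.8 − 10)/18 − 2.6 = 5.56. Sum of squares 1184.1 + 1.778 × 14.8² = 1573.5, SD 7.24, SE 2.581. Result 5.6 (0.3 to 10.8, p = 0.040).
- Opposite direction, two Sham worsening by 5: 9.8 − (36.4 − 10)/16 = 8.15 (3.4 to 12.9).
- Both arms, two each at zero change: 156.8/18 − 36.4/16 = 6.44 (1.9 to 11.0).
- Zero-change Active losses needed to cross p = 0.05: five give 4.87 (p = 0.048), six give 4.53 (−0.2 to 9.3, p = 0.062). Six would be 6/22 = 27% of Active and 36 children enrolled, when Section 5.0 says "We anticipate to screen about 40 participants to recruit 30 participants for the study". That is extreme.

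**The case against.** **No loss is documented.** The SAP describes ratings for all participants, 16 + 14 equals the planned 30, and no final CARS is missing. This stands. A reader might infer from the limitation to children who completed, or from 16:14 where strict alternation of 30 gives 15:15, that children left and were replaced. The documents do not support that: replacement would also restore 30, but neither feature shows that it occurred. Part of the SAP was not available for this review and may give the flow and the analysis set, so its absence cannot count against the plan.

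**The retention sentence is narrow.** It follows two triggers only and sits in a participant-risk table. It is not an analysis-set rule, and it would be wrong to read it as governing every withdrawal. This stands. The gap is that no route out of treatment, under any section, comes with a planned CARS.

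**Regress is limited.** Section 15.0 stops the whole study if two children suddenly regress, so that route cannot produce many leavers. Recent severe aggression or self-injury is also an exclusion. Both points stand and argue against large one-sided losses.

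**Matching might allocate a replacement.** One could read Sections 5.0, 7.3 and 14.0 as giving the new child the vacated place. The text does not say so, and such a place would be filled without randomisation. The gap remains.

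**The trial has reported.** A protocol change cannot alter these data. This stands and limits the protocol part of the point to further enrolment.

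**Conclusion.** The point holds as a conditional one. Applied as written, the withdrawal and replacement rules lead, by inference, to a comparison of completers and replacements. That biases the CARS difference only if leaving relates to both arm and outcome, and it can do so in either direction. Under assumed one-arm losses of 10% to 20%, graded selection shifts the difference by about 0.6 to 1.3 points, with ceilings of 1.3 and 2.3. These figures rest on an SD of 6.50 recovered from the reported interval, normal changes and invented loss counts.

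A reader might conclude that the reported 7.23 is biased or its significance unsafe. The documents do not support that. Two adverse Active losses would leave 5.6 to 6.1 points with an interval above zero, so a few losses mainly change the size of the effect. Significance goes only in adverse, one-sided cases.

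Minor for the existing data, where it is a query; should be fixed only for further enrolment under this protocol.

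**What to change.** **Existing data.** State the numbers randomised, withdrawn and replaced, by arm and reason. If none withdrew, or the SAP already says so, the point is closed. Otherwise make all randomised children the primary set and add a tipping-point analysis that varies both arms, including zero-change and symmetric scenarios. Cost: one flow statement, and a short sensitivity analysis only if someone left.

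**Protocol, for any further enrolment.**
- When treatment stops, seek the end-of-study CARS at the time originally planned, with parental permission and from the existing blinded rater.
- Amend the retention sentence in Section 13.0 for consenting families.
- Allocate any additional child from an extended, concealed random list.
- Keep the original child in the analysis, in the assigned arm.

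Families who leave all components stay unobserved, as Section 8.0 requires. The clinical withdrawal rules are not in question. Cost: some wording, a few extra CARS ratings, and possibly a smaller or less precise estimate.

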**Transcranial Photobiomodulation for
reducing autism symptoms in
children.**

October 1, 2020

PROTOCOL TITLE:

Transcranial photobiomodulation for reducing autism symptoms in children.

PRINCIPAL INVESTIGATOR:

Name	[name]
Department	N/A
Phone Number	

CO-INVESTIGATORS:

Name	[name]
Department	N/A
[contact]

Name	[name], CFA, Esq.
Department	N/A
[contact]

1.0 Purpose of the study:

The purpose of this 8-week open label feasibility study is to assess the tolerability, safety and efficacy of Transcranial LED Therapy for language learning and reducing symptoms of autism in children.

The investigators propose to enroll up to 30 participants of both genders ages 24 months to 6 years who have been previously diagnosed with moderate to severe ASD by licensed professionals according to the Diagnostic and Statistical Manual of Mental Disorders, Fifth Edition (DSM-5) criteria for Autism Spectrum Disorder (ASD).

The hypothesis to be tested is that exposure to photobiomodulation and speech parsing program will reduce children's symptoms of autism, such as delays in language production and comprehension, anxiety, tantrums, limited eye-contact and improve responsiveness.

2.0 Background / Literature Review / Rationale for the study:

2.1 Background Science of Photobiomodulation and Rationale:

There are several studies that suggest that mitochondrial energy disturbance is an underlying mechanism of autism, for at least some of the children. Specifically, Weisman, Kelley, Bauman, Cohen, Murray, Mitchell and Kern (2008) looked at the medical records of 25 children diagnosed with autism and found that "Levels of blood lactate, plasma alanine, and serum ALT and/or AST were increased at least once in 76%, 36%, and 52% of patients, respectively". Furthermore, 2 out of those 25 people had rare mtDNA mutations. The authors concluded that at least for a subset of ASD children, mitochondrial disturbances in energy production could be the underlying mechanism. Furthermore, Giulilvi, Zhang, Omanska-Klusek, Ross-Intra, Hertz-Picciotto, Tasson and Pessach (2010), looked at biochemical markers of ASD kids (2-5yo), and concluded that ASD children are more likely to have Mitochondria dysfunction, mtDNA replication and mtDNA deletion than neurotypical ones.

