We are developing a safe and effective protocol for administering tPBM via a wearable device. This physical device is getting developed by JelikaLite LLC. The parameters are developed by [name] (the PI of this study), [name] (leading photobiomodulation expert from Harvard Medical School and an advisor to JelikaLite), [name] (leading neuroscientist who is studying photobiomodulation at Boston Medical University and an advisor to JelikaLite), and [name] (an industrial product designer with over 30 years of expertise in designing medical devices). The purpose of this feasibility study is to evaluate the safety and comfort of the product, as well as preliminary efficacy of the treatment effect. The device will stimulate Default Mode Network (to increase brain connectiveness) as well as Broca and Wernike areas (to facilitate speech comprehension and production) and Occipital lobe (as many ASD children rely on visual information for language learning). The device will be physically light, comfortable to wear for children and could eventually be used at home as frequently as necessary.

The reason why the device may be helpful to children is because of the science of photobiomodulation. The device will have embedded LED lights in it, which will shine red light and near infra red lights. The children will wear the device for approximately 5-10 minutes, twice a week (closely replicating the protocol of Leisman et al as well as the clinical study at MGH). The light stimulates mitochondrial ATP production. Only about 2% of the light penetrates the skull. However, because brain is the largest energy consuming organ of the body, even those 2% result in significant

improvement of the symptoms (even small boost in ATP production results in significant improvement). Having more energy enables the brain cells to heal, grow and form new neural connections. Other benefits of tPBM is increased blood flow to the brain, which increase brain oxygen supply and reduce inflammation.

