9.0 Recommendation for Only One Parent Consent

Both this proposed study and the investigational device do not involve greater than minimal risk.

Rationale for the device:

Safety of Photobiomodulation: Photobiomodulation has been extensively studied on humans for more than 30 years, including its use for neurological conditions. There are several photobiomodulation products (for neurological conditions) that are on currently on the market (using both LED and Lasers). The consumers report no side-effects.

After more than three decades of research there are no known major side effects attached to photobiomodulation therapy.

Rare Minor Side effects for first time users only include: Tiredness (temporary) – probably due to the release of metabolites but the majority report a resurgence of energy. Headaches (temporary) – from the reactivation of neural connections and increased microcirculation.

Safety Issues of our product specifically: Our product emits non-laser based irradiation (incoherent light) with a low level energy intensity. Infrared emits non-laser based irradiation (incoherent light) with a low level energy intensity. We use 850 nm. The participants might perceive slight warm. No other perceptions will be produced by wearing the device. No feelings of discomfort are anticipated (the device is especially made for children, it's very comfortable and soothing to wear). There are no known side-effects of photobiomodulation (with 30 years of research and studies, including research on 5 year old children diagnosed with ASD).

Rationale for the study:

The study activities include: 1) wearing the device and / or 2) Listening to the audio program which provides language acquisition input or 3) free play while listening to nursery rhymes. In addition, the parents will be interviewed about the child's behavior on a weekly basis.

None of these activities present greater than minimal risk to the health and well-being of the participants.

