We will conduct weekly interviews with the parents, asking them questions about child's behavior and functioning to collect both safety and efficacy data. The interviews will be conducted either by telephone or in person (per parental choice). Please attached interview protocol. [name], a licensed clinical psychologist will review the data. The detailed qualitative data will be collected. No statistical analysis is necessary.

If a participant shows sudden developmental regress, we will recommend immediate neurological evaluation and his/her participation will be discontinued (unless this participant has been manifesting regress prior the start of the study). If two participants suddenly manifests signs of regress (not anticipated, not seen before in prior photobiomodulation studies), we will immediately discontinue the study.

16.0 Data, and if applicable, Specimen Banking:

The raw research data will be stored for 6 years. The identifying parental information will be kept for a year, for potential follow up interviews. The consent form will include their permission to keep identifying data for a year.

Although we do not plan to re-contact the participants after the study is complete, a follow up interview in 6 months or a year could be useful to assess the sustainability of the benefits of photobiomodulation. In this case, we will be applying for a separate IRB (minimal risks) to conduct the follow up interview. Presently, we do not plan to do it (although we recognize that it could potentially be useful for research purposes).

The data will be stored in encrypted, password protected files in a secure cloud.

17.0 Data Sharing:

Only aggregated data will be shared with scientific community (via publications). Only aggregated data will be shared with potential investors. If individual data (e.g., from an interview) is shared for illustrative purposes, identifying information will NOT be shared (STUDY ID will be assigned to each participant).

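### Safety and tolerability are first-named purposes but have no endpoint or by-arm summary in the text available, so only a narrative safety statement is planned for

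*Protocol*

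**What the plan says.** Protocol section 1.0 gives the purpose as to "assess the tolerability, safety and efficacy of Transcranial LED Therapy for language learning and reducing symptoms of autism in children". Section 2.2 repeats the order for the device: to "evaluate the safety and comfort of the product, as well as preliminary efficacy of the treatment effect".

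Section 15.0 describes weekly parent interviews, "asking them questions about child's behavior and functioning to collect both safety and efficacy data", reviewed by a licensed psychologist. It then states "No statistical analysis is necessary". The next paragraph discontinues a child who shows sudden regress and stops the study after two such children.

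Section 7.7 makes total CARS2 the quantitative outcome, adds EEG, and names an analysis for each. Of the interviews it says "Qualitative data will be used for information purposes and will supplement quantitative data". The confidentiality paragraph in 7.8 allows qualitative data to be reported only as illustration.

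The interview topics in 7.7 include "number of words they can produce, eye-contact, anxiety, frequency of tantrums, eating, and difficulties falling asleep". Section 9.0 names temporary tiredness and temporary headache as possible effects. Section 13.0 foresees that a child may take the headband off before the session ends.

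The SAP text available covers baseline data and CARS only.

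**The concern.** Two of the three stated aims have no variable, event definition or tabulation attached to them. The one sentence on analysing the safety data says that none is required.

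The consequence is practical. If no parent happens to mention a headache, the report will read as though none occurred, although the parents may never have been asked. Without counts by arm, a reader also cannot tell whether tiredness, distress or refusal of the headband was more common with the lights on than with the sham device. The protocol already holds that photobiomodulation has no known side effects (sections 9.0 and 13.0), so an uncounted account would tend to confirm what was assumed at the start. The sham arm and the weekly contact that would allow a proper description are already in the design.

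**Working it through.** **1. Each aim against its measure and analysis**

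| Aim | Measure in the text | Planned summary |
|---|---|---|
| Efficacy | Total CARS2; EEG (7.6, 7.7) | Mixed-design ANOVA and t-tests (7.7); t-test on change and a responder comparison (SAP) |
| Safety | Weekly interviews and parent diary (7.7, 15.0), no defined event | None; 15.0 says none is necessary |
| Tolerability, comfort | Early removal described as a risk (13.0), no variable | None |

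The list of study data in section 14.0 has consent forms, CARS2 scores and interview data, with no adverse-event log or session record. That list is not exhaustive, since it also omits EEG and the diaries, so it is supporting evidence only.

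**2. Named harms against listed topics**

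Headache is in neither the interview topics nor the diary topics in 7.7. Tiredness is touched only indirectly, through sleep. The script itself is an attachment that was not available.

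**3. Route for early removal into the data**

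Under 7.8 the researcher in the treatment room does not conduct the interviews, and the interviewer is not in the room. The person who sees a headband come off is therefore not the person who records parent data, and no session log is described.

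**4. What counts could show**

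The documents give no safety rate, margin or sample size, so there is no safety figure to reproduce. The inputs are 15 children per arm (section 5.0) and 16 active children analysed (SAP, Primary Outcome). The event rates below are assumptions.

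Exact upper limit with zero events in n:
- n = 15, two-sided 95%: 1 − 0.025^(1/15) = 0.218
- n = 15, one-sided 95%: 1 − 0.05^(1/15) = 0.181
- n = 16: 0.206 two-sided and 0.171 one-sided

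One event in 15 gives an exact 95% interval of 0.2% to 31.9%.

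Chance of seeing at least one event in 15 children, 1 − (1 − p)^15:
- p = 1%: 14%
- p = 5%: 1 − 0.95^15 = 1 − 0.463 = 54%, so a 46% chance of seeing none
- p = 10%: 79%
- p = 20%: 1 − 0.8^15 = 0.965, about 96%

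Between-arm test for 5% v 20%, 15 per arm, two-sided 5%, normal approximation with pooled null variance (mean rate 0.125):
- null SE = √(2 × 0.125 × 0.875 / 15) = 0.1208
- alternative SE = √((0.05 × 0.95 + 0.20 × 0.80) / 15) = 0.1176
- power = Φ[(0.15 − 1.96 × 0.1208) / 0.1176] = Φ(−0.74) = 23%
- 80% power would need 76 per arm

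A formal test would add little. Counts with intervals are feasible and show what the sample leaves open.

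**The case against.** The strongest reply is that the sentence sits in a monitoring section and may mean only that week-to-week review is clinical and not statistical. That reading is fair. A reader might infer that the protocol forbids any safety analysis at the end of the trial; the sentence does not establish that. The gap does not depend on it, however, because 7.7 and 7.8 separately confine interview data to information and illustration, and no other safety summary appears in the text available.

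A reader might also infer that the plan yields no counts or denominators, or that the trial can support no safety statement at all. Neither follows. The two-child regress rule requires counting, as do the withdrawals for aggression or self-injury in 13.0. Arm sizes are planned, interview data are held under Study ID, and a psychiatrist has oversight. Events could be tabulated by arm, and a limited descriptive statement is possible in a 30-child feasibility study. What is missing is a specified table and assurance that the relevant events are recorded.

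It would also be wrong to present the 22% limit and the 46% chance of seeing no event as harm caused by the missing analysis. Both follow from 15 exposed children and would be the same after the change.

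Finally, the interview script and the part of the SAP before its primary-analysis section were not available. The script may already ask about headache or tiredness, and a safety analysis in the missing SAP text cannot be excluded. Those reservations stand.

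**Conclusion.** The point holds in a limited form. In the text available, safety and tolerability have no endpoint, no adverse-event definition and no by-arm summary, although they are named ahead of efficacy. Followed as written, the plan leads to a narrative safety account. It does not provide for a quantified statement, a comparison with sham, or a claim that uncommon harms are absent.

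In size, zero events in 15 active children leaves true rates up to about 22% compatible with the data (21% with 16). An effect occurring in 5% of children would have a 46% chance of not appearing among 15. These figures assume independent children and complete ascertainment; if parents are not asked, the real uncertainty is larger.

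The conclusion rests on the absence of contrary text in the unavailable script and SAP opening. It should be corrected before the safety results are written up, but it does not undermine the trial's efficacy analysis.

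**What to change.** Replace the sentence in section 15.0 with a descriptive analysis, and repeat it in the SAP:

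- By arm, the number and percentage of children with headache, tiredness, developmental regress, withdrawal for aggression or self-injury, or any other adverse event, each with an exact 95% confidence interval.
- By arm, the proportion of sessions in which the headband came off early.
- A stated denominator: every child who began at least one session, including those who later withdrew, because section 5.0 allows dropouts to be replaced.
- No significance test.
- A sentence in the report saying that zero events in 15 active children is compatible with a rate up to about 22%.

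If the script does not already do so, ask about headache, tiredness and device discomfort in the existing weekly interview. Have the researcher in the room log early removal at each session. Sections 2.2 and 7.5 do not give one planned wear time for both arms; they must be reconciled before a removal can be classed as early.

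The cost is a few questions in an interview already held, one log entry per session and one table. The downside for the sponsor is that the safety wording will have to be more cautious.
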